15.0 REGULATORY CONSIDERATIONS

15.1 Institutional Review Board/Ethics Committee approval

The protocol for this study has been designed in accordance with the general ethical principles outlined in the Declaration of Helsinki. The review of this protocol by the IRB/EC and the performance of all aspects of the study, including the methods used for obtaining informed consent, must also be in accordance with principles enunciated in the declaration, as well as ICH Guidelines, Title 21 of the Code of Federal Regulations (CFR), Part 50 Protection of Human Subjects and Part 56 Institutional Review Boards.

The Investigator will be responsible for preparing documents for submission to the relevant IRB/EC and obtaining written approval for this study. The approval will be obtained prior to the initiation of the study.

The approval for both the protocol and informed consent must specify the date of approval, protocol number and version, or amendment number.

Any amendments to the protocol after receipt of IRB/EC approval must be submitted for approval by the Investigator to the IRB/EC. The Investigator is also responsible for notifying the IRB/EC of any serious deviations from the protocol, or anything else that may involve added risk to subjects.

Any advertisements used to recruit subjects for the study must be reviewed and approved by the IRB/EC prior to use.

15.2 Informed Consent Procedures

The Investigator must obtain informed consent of a subject or his/her designee prior to any study related procedure as per GCP's as set forth in the CFR and ICH guidelines.

Documentation that informed consent occurred prior to the subject's entry into the study and the informed consent process should be recorded in the subject's source documents. The original consent form, signed and dated by the subject and by the person consenting the subject prior to the subject's entry into the study, must be maintained in the Investigator's study files. At the pre-admission consultation, patients will be fully informed as to the purposes and potential risks and benefits involved in this study. Patients will have ample opportunity to ask questions before consenting. Legal guardians will sign informed consent for legally incompetent patients in accordance with hospital policy.

15.3 Protecting Privacy and Confidentiality

Confidentiality will be maintained within the limits of the law. Patient names or any other identifying information will not be used in reports or publications resulting from this study. Only qualified staff from New York Presbyterian Hospital, Weill Medical College of Cornell University, the Food and Drug Administration, or other study support such as the National Cancer Institute will be able to review patient medical records.

Celgene Pharmaceuticals, Inc. affirms the subject's right to protection against invasion of privacy. In compliance with United States federal regulations, Celgene requires the Investigator to permit Celgene's representatives and, when necessary, representatives of the FDA or other regulatory authorities to review and/or copy any medical records relevant to the study in accordance with local laws.

Should direct access to medical records require a waiver or authorization separate from the subject's statement of informed consent, it is the responsibility of the Investigator to obtain such permission in writing from the appropriate individual.

15.4 Study records requirements

The Investigator must ensure that the records and documents pertaining to the conduct of the study and the distribution of the study drug, that is copies of CRFs and source documents (original documents, data, and records [e.g., hospital records; clinical and office charts; laboratory notes; memoranda; subject's diaries or evaluation checklists; pharmacy dispensing records; recorded data from automated instruments; copies or transcriptions certified after verification as being accurate copies; microfiches; photographic negatives, microfilm, or magnetic media; x-rays; subject files; and records kept at the pharmacy, at the laboratories, and at medico-technical departments involved in the clinical study; documents regarding subject treatment and study drug accountability; original signed informed consents, etc.]) be retained by the Investigator for as long as

needed to comply with national and international regulations (generally 2 years after discontinuing clinical development or after the last marketing approval). The Investigator agrees to adhere to the document/records retention procedures by signing the protocol.

15.5 Protection of Human Rights

Participation in this trial is voluntary. All patients will be required to sign a statement of informed consent, which must conform to Weill Cornell Medical College IRB guidelines.

Patients will be eligible for this trial regardless of gender or racial/ethnic background. All patients must follow the guidelines for pregnancy testing, birth control and counseling related to the risk of fetal exposure to lenalidomide as outlined in Appendix III.

15.6 Premature Discontinuation of Study

The responsible local clinical investigator, as well as Celgene, has the right to discontinue this study at any time for reasonable medical or administrative reasons in any single center. Possible reasons for termination of the study could be but are not limited to:

- Unsatisfactory enrollment with respect to quantity or quality.
- Inaccurate or incomplete data collection.
- Falsification of records.
- Failure to adhere to the study protocol.

15.6.1 Study as a whole

Celgene reserves the right to terminate this clinical study at any time for reasonable medical or administrative reasons.

Any possible premature discontinuation would be documented adequately with reasons being stated, and information would have to be issued according to local requirements (e.g. IRB/EC, regulatory authorities, etc.).

15.7 Benefits of the Protocol

The potential benefit of this study is the development of a safe and effective treatment program for newly diagnosed MM patients. Knowledge will be acquired about this treatment program, its tolerability, and the effectiveness of clarithromycin (Biaxin[®]), lenalidomide (Revlimid[®]), and dexamethasone (Decadron[®]) in the treatment of newly diagnosed MM. If effective, this treatment plan may improve remission rates in newly diagnosed MM patients and hopefully prolong the disease survival.

15.8 Risks in Relation to Anticipated Benefit

The risks associated with participation in this trial are commensurate with the expected risks of other potential therapies and are reasonable given the potential benefit to patients

with newly diagnosed MM. If the combination of Car-BiRD is as effective against newly diagnosed MM as anticipated, this regimen could become standard of care leading to improved survival.

15.8 Alternative Treatments

Patients who refuse to participate in the study or decided to withdrawal from the study will be given the option to choose standard chemotherapy, other investigation studies, supportive care, or no anti-cancer treatment at all. Some patients treated with standard chemotherapy do benefit. Treatment with thalidomide, lenalidomide, bortezomib, or other cytotoxic chemotherapy alone or in combination with corticosteroids has prior proven efficacy. (While the results of this therapy have been encouraging, long-term remissions are rare, no patients are cured and none of the drugs used in these standard treatments are free of side effects. We believe that this novel regimen will improve response rates and duration of remission.

15.9 Incentives

No incentives will be offered to patients/subjects for participation in the study. Participation is voluntary.

APPENDIX I: Criteria for Response

Table 1: Criteria for Response, Disease plateau, and Disease Relapse as adopted from the EBMT and the international uniform response criteria³⁵

Stringent Complete Response (sCR) requires all of the following:

  All of the criteria of complete response  Normal serum free light chain ratio  Absence of monoclonal cells on bone marrow aspirate by immunohistochemistry or immunofluorescence
Complete Response (CR) requires all of the following:

  Absence of the original monoclonal protein in serum and urine by immunofixation. The presence of oligoclonal bands consistent with oligoclonal immune reconstitution does not exclude CR.  ≤5% plasma in a bone marrow aspirate and also on trephine bone biopsy, if biopsy is performed. If absence of monoclonal protein is sustained for 6 weeks it is not necessary to repeat the bone marrow, except in patients with non-secretory myeloma where the marrow examination must be repeated after an interval of at least 6 weeks to confirm CR.  No increase in size or number of lytic bone lesions (development of a compression fracture does not exclude response)  Disappearance of soft tissue plasmacytoma.
Very Good Partial Response (VGPR) requires all of the following:

  Negative serum and urine protein electrophoresis with persistence of monoclonal protein detectable on immunofixation OR  ≤90% reduction in serum monoclonal protein level with urine monoclonal protein level < 100mg in 24 hour collection.
Partial Response (PR) requires all of the following:

  ≥50% reduction in the level of the serum monoclonal paraprotein.  Reduction in 24h urinary light chain excretion either by ≥90% or to <200mg.  For patients with light chain only disease, then a 50% reduction in the difference between the involved and unininvolved free light chain level may be substituted for the M-protein measurement.  For patients with non-secretory myeloma only, ≥50% reduction in plasma cells in a bone marrow aspirate and on trephine bone biopsy, if biopsy is performed.  ≥50% reduction in the size of soft tissue plasmacytomas (by radiography or clinical examination).  No increase in size or number of lytic bone lesion (development of a compression fracture does not exclude response)
Stable Disease (SD) requires the following:

  Not meeting the criteria stringent complete response (sCR), complete response (CR), very good partial response (VGPR), or partial response (PR)
Plateau:

  Stable values (within 25% above or below value at the time response is addressed) 
Patients in which no significant change (<50% decrease or <25% increase from baseline) in the production rate of the monoclonal serum protein or Bence-Jones protein excretion and no new lytic lesions and/or plasmacytomas are detected.

Relapse from CR requires at least one of the following:

- Reappearance of serum or urinary paraprotein on immunofixation or routine electrophoresis, confirmed by at least one further investigation and excluding oligoclonal immune reconstitution.
- ≥5% plasma in a bone marrow aspirate or trephine bone biopsy.
- Development of new lytic lesions of soft tissue plasmacytomas or definite increase in the size of residual bone lesions (development of a compression fracture does not exclude continued response and may not indicate progression).
- Development of hypercalcemia (corrected serum calcium >11.5mg/dl or 2.8 mmol/l) not attributable to any other cause.

Progressive disease (PD) for patients not in CR requires one or more of the following:

- >25 increase in the level of the serum monoclonal paraprotein, which must also be an absolute increase of at least 5g/L and confirmed by at least one repeated investigation.
- >25 increase in the 24h urinary light chain excretion, which must also be an absolute increase of at least 200mg/24h and confirmed by at least one repeated investigation.
- >25% increase in plasma cells in a bone marrow aspirate and on trephine bone biopsy, which must also be an absolute increase of at least 10%.
- Definite increase in the size of existing bone lesions or soft tissue plasmacytomas.
- Development of new bone lesions or soft tissue plasmacytomas (development of a compression fracture does not exclude continued response and may not indicate progression).
- Development of hypercalcemia (corrected serum calcium >11.5mg/dl or 2.8 mmol/l) not attributable to any other cause.

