5.0 CRITERIA FOR PATIENT ELIGIBILITY

5.1 Inclusion Criteria

Each subject must meet all of the following inclusion criteria to be eligible to participate in this study:

- Subject must voluntarily sign and understand written informed consent.
- Subject is ≥ 65 years at the time of signing the consent form.
- Subject has histologically confirmed multiple myeloma that has never before been treated (see Appendix II).
- Subject has no prior anti-myeloma treatment therapy within 14 days prior to initiation of study treatment except for corticosteroids with a maximum allowed dosage equivalent to three pulses of dexamethasone (40mg daily for 4 days equals one pulse). Patients may have received prior adjuvant antiresorptive therapy (i.e., pamidronate or zoledronic acid) as routine care, or radiation therapy as palliation for pain and/or spinal cord compression.
- Subject has measurable disease as defined by > 0.5 g/dL serum monoclonal protein, > 10 mg/dL involved serum free light chain (either kappa or lambda) provided that the serum free light chain ratio is abnormal, > 0.2 g/24 hrs urinary M-protein excretion, and/or measurable plasmacytoma(s) of at least 1cm in greatest dimension as measured by either CT scanning or MRI.
- Subject has a Karnofsky performance status $\geq 60\%$ ($> 50\%$ if due to bony involvement of myeloma (see Appendix IV).
- Subject is able to take prophylactic anticoagulation as detailed in section 9.1 (patients intolerant to aspirin may use warfarin or low molecular weight heparin).
- Subject is registered into the mandatory RevAssist® program, and is willing and able to comply with the requirements of RevAssist® program.
- If subject is a female of childbearing potential (FCBP),† she must have a negative serum or urine pregnancy test with a sensitivity of at least 25 mIU/mL within 10 – 14 days prior to and again within 24 hours of prescribing lenalidomide (prescriptions must be filled within 7 days) and must either commit to continued abstinence from heterosexual intercourse or begin TWO acceptable methods of birth control, one highly effective method and one additional effective method AT THE SAME TIME, at least 28 days before she starts taking lenalidomide. FCBP must also agree to ongoing pregnancy testing. Men must agree to use a latex condom during sexual contact with females of child bearing potential even if they have had a successful vasectomy. See

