14.4 Analysis of Secondary Endpoints

Secondary endpoints include objective response rate (CR+PR) and complete response rate (CR) (estimated via binomial proportions), and Kaplan-Meier overall survival. Overall survival will be defined as the time from randomization day until death. Ninety-five percent confidence intervals will be calculated for the objective response proportion in each group via binomial proportions. Comparison of the objective response rate and complete response rate between the treatment groups will be performed by the chi-square test. The comparison of the overall survival distributions between the treatment groups will be performed by the log-rank test. Analysis of these three secondary endpoints will

be considered hypothesis-generating only and will be adjusted for multiplicity of outcomes by the Bonferroni method. In the event that no significant result is observed for the primary endpoint (PFS), significant findings for the secondary endpoints (even after correction for multiplicity of outcomes) will not result in efficacy claims for labeling purposes. Similarly, if a significant finding is observed for the primary endpoint, significant findings for the secondary endpoints will still not result in efficacy claims for labeling purposes. All other secondary endpoints (i.e., event-free survival, duration of response, time to progression, progression-free survival 2, and quality of life measures) will only be descriptively presented for each treatment group and no formal statistical comparison will be made between treatment arms. Confidence intervals for the secondary endpoints of objective response rate, complete response rate, and overall survival will be Bonferroni-corrected. The frequency of subjects experiencing toxicities will be tabulated. Toxicities will be assessed and graded according to CTCAE v. 4.0 terminology. Exact 95% confidence intervals around the toxicity proportions will be calculated to assess the precision of the obtained estimates.

All p-values will be two-sided with statistical significance evaluated at the 0.05 alpha level. P-values will be Bonferroni-corrected for the secondary endpoints of objective response rate, complete response rate, and overall survival. All analyses will be performed in SAS Version 9.4 (SAS Institute, Inc. Cary, NC) and Stata Version 14.0 (StataCorp, College Station, TX).

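### The complete response criteria carry no serum free light chain condition, so some patients who enter on free light chains alone can be counted as complete responders while that marker is still abnormal.

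*Combined protocol and SAP*

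**What the plan says.** **Entry.** Section 5.1 lists four kinds of measurable disease joined by and/or. One is an involved serum FLC above 10 mg/dL, "provided that the serum free light chain ratio is abnormal". A patient can therefore enter on FLC alone, with no measurable serum or urine M-protein.

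**Response.** Appendix I defines CR by four items, all required:
- protein: "Absence of the original monoclonal protein in serum and urine by immunofixation";
- marrow: "≤5% plasma in a bone marrow aspirate and also on trephine bone biopsy, if biopsy is performed";
- bone: "No increase in size or number of lytic bone lesions (development of a compression fracture does not exclude response");
- plasmacytoma: "Disappearance of soft tissue plasmacytoma".

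FLC appears in the level above and in a level below. Stringent CR adds "Normal serum free light chain ratio". PR has a substitute item: "For patients with light chain only disease, then a 50% reduction in the difference" between involved and uninvolved light chains.

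**Analysis.** Section 14.4 names objective response rate (CR+PR) and "complete response rate (CR) (estimated via binomial proportions") among the secondary endpoints. Both are compared between arms by chi-square with a Bonferroni correction over three endpoints, and both are labelled hypothesis-generating.

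**The concern.** For a patient who enters on FLC alone and is immunofixation-negative at baseline, the protein item for CR is met before treatment starts and says nothing about treatment effect. If there is no plasmacytoma and no new bone change, marrow at or below 5% is the only item left to satisfy. The marker that made the patient eligible is not consulted, so it may still be abnormal when CR is recorded.

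Appendix I takes FLC into account at stringent CR and at PR but not at CR. Responses labelled CR on this basis enter two of the three formally tested secondary endpoints. They also bring the patient into minimal residual disease testing, which Section 4.1 reserves for complete responders.

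**Working it through.** **1. Does any other text close the gap?** Section 1.3 and Section 10.3 schedule serum FLC on day 1 of each cycle, but neither links the result to CR. Section 10.3 calls for a marrow to confirm CR, which is the marrow item again. No section adds an FLC condition to CR.

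**2. How would such a patient be classed?** Two readings are possible.
- *Light chain only.* The term is used in the PR criteria but not defined. On this reading a patient can satisfy the CR items while the FLC difference has fallen by less than 50%, and so may not meet the FLC item for PR.
- *Non-secretory.* Note b to the symptomatic-myeloma table in Appendix II calls disease non-secretory when no monoclonal protein is detected, and then asks for at least 30% marrow plasma cells and/or a biopsy-proven plasmacytoma. A fall from 30% to 5% is (30 − 5)/30 = 83%, which exceeds the 50% marrow reduction in the PR item for non-secretory disease. CR also then needs a second marrow at least 6 weeks later.

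On either reading, CR is decided without FLC.

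**3. The plan's own figure.** The plan has no design calculation for CR. Its PFS calculation (Section 14.2: 133 events, hazard ratio 1.75, 90% power, two-sided 0.05) is reproduced closely by the Schoenfeld formula: 4 × (1.960 + 1.282)² / (ln 1.75)² = 134.2, so 135 events. CR does not enter it.

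**4. Size.**

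Inputs from the documents:
- CR rates of 45.8% (BiRd) and 13.9% (Rd), from the case-matched analysis in Section 3.8;
- 153 patients per arm, from Section 14.2;
- alpha of 0.05/3 = 0.0167, from Section 14.4.

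Inputs assumed, because the documents give neither:
- f = 5% to 15%, the share of patients who are both measurable by FLC only and immunofixation-negative;
- q = 20% to 50%, the share of those patients' non-CRs that the present wording counts as CR, equal in both arms.

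The Section 3.8 rates are taken as the true rates, applying to this subgroup as to the rest.

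Formulas: observed CR = p + f·q·(1 − p); extra CRs per arm = 153·f·q·(1 − p).

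| | BiRd | Rd | Difference | Odds ratio | Extra CRs |
|---|---|---|---|---|---|
| True | 45.8% | 13.9% | 31.9 points | 5.23 | 0 |
| f·q = 0.05 × 0.2 = 0.010 | 46.3% | 14.8% | 31.6 points | 4.99 | 0.8 + 1.3 = 2.1 |
| f·q = 0.15 × 0.5 = 0.075 | 49.9% | 20.4% | 29.5 points | 3.89 | 6.2 + 9.9 = 16.1 |

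Power for the CR comparison at alpha 0.0167 stays above 99.9% throughout.

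**5. A smaller contrast.** Section 3.8 also reports 30% CR with BiRd in phase II. Setting that against 13.9% pairs two different analyses, so it is only a sensitivity case. Over the same range of f·q, the difference falls from 16.1 to 15.9–14.9 points, power falls from 84.8% to 82.9–69.9%, and about 2 to 18 patients are affected.

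**6. Unequal fractions.** Take f = 15% and the 45.8% vs 13.9% rates. With q = 50% in BiRd and 20% in Rd, the rates are 49.9% and 13.9% + 0.03 × 86.1% = 16.5%, and the difference widens to 33.4 points. With the two values of q exchanged, the rates are 45.8% + 0.03 × 54.2% = 47.4% and 20.4%, and the difference narrows to 27.1 points.

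**The case against.** The strongest reply is that the protein item alone does not confer CR. The bone and plasmacytoma items also apply, and a patient who entered with at least 10% clonal marrow plasma cells must at least halve that to reach 5%. That is a real response in the marrow, and Appendix II note b supports classing the patient as non-secretory, with a repeat marrow as a safeguard. All of this stands. It narrows the problem but does not remove it, because none of these items looks at FLC.

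The words on the original protein might also be read as presupposing one that immunofixation can detect at baseline. The text then gives such patients no protein rule for CR, which also needs repair.

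A reader might infer three stronger things:
- *That CR rests on immunofixation and marrow alone.* Appendix I has four items.
- *That these patients are CR without reaching PR.* This depends on classing them as light chain only. Under the non-secretory reading the marrow item could support PR.
- *That the CR contrast is necessarily diluted.* This needs equal fractions in both arms. The fraction depends on marrow clearance, which treatment may affect, so the direction is uncertain.

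Nor is everyone measurable by FLC only affected. The serum and urine thresholds in Section 5.1 are quantitative, so a patient below them may still be immunofixation-positive at entry, and for that patient the protein item works. Finally, FLC normalisation has its own tier in stringent CR. That tier does not supply the missing condition, because CR itself is the tested endpoint.

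**Conclusion.** The rule is wrong as written, with low-to-moderate severity. Followed literally, it counts some patients as CR while their only measurable entry marker is abnormal, and it carries them into the tested CR rate and objective response rate.

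The number affected cannot be fixed from the documents. Under the stated assumptions it is about 2 to 16 of 306 patients at the case-matched CR rates. The test would barely notice this if the true contrast is that large, and could lose noticeable power if it is nearer 30% vs 13.9%. Both CR rates are inflated whenever such cases occur.

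The consequences are limited. Section 14.4 treats the secondary tests as hypothesis-generating and rules out labelling claims from them, and the PFS sample size and event count do not change.

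**What to change.** Add one condition to the CR criteria in Appendix I: *for patients whose measurable disease at entry is by serum free light chains only, a normal serum free light chain ratio is also required.* In the PR criteria, state that these patients are assessed under the light-chain item and not under the non-secretory item, so that the class is settled before any response is read.

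No new test, visit or sample size change is needed, since serum FLC is already measured every cycle. The costs are a possibly slightly lower CR rate in both arms and, in this subgroup, a narrower gap between CR and stringent CR, which would then differ only by the absence of monoclonal cells in the marrow.

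### Appendix I prints the VGPR serum threshold as a fall of at most 90%, which breaks the order of the response categories; the 5% marrow limits and the ORR definition also need clarifying

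*Combined protocol and SAP*

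**What the plan says.** Section 2.2 makes Appendix I the definition of response, and Section 10.11 points to the same appendix for progression as a reason for removal from study.

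- **VGPR** has two alternatives joined by OR. One is negative electrophoresis with protein still seen on immunofixation. The other is "≤90% reduction in serum monoclonal protein level with urine monoclonal protein level < 100mg in 24 hour collection".
- **PR**, the next category down, needs "≥50% reduction in the level of the serum monoclonal paraprotein" and "Reduction in 24h urinary light chain excretion either by ≥90% or to <200mg", with further conditions on plasmacytomas and bone lesions.
- **SD** is the residual category: "Not meeting the criteria stringent complete response (sCR), complete response (CR), very good partial response (VGPR), or partial response (PR").
- **CR** allows "≤5% plasma in a bone marrow aspirate and also on trephine bone biopsy, if biopsy is performed". **Relapse from CR** needs only one item from its list, and one item is "≥5% plasma in a bone marrow aspirate or trephine bone biopsy".
- **sCR** starts from "All of the criteria of complete response".

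Section 14.4 states: "Secondary endpoints include objective response rate (CR+PR) and complete response rate (CR"). ORR and the CR rate are each compared between arms by a chi-square test. Together with overall survival they are Bonferroni-corrected, and they are described as exploratory, with no labelling claim whatever the primary result.

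**The concern.** A higher response category should be harder to reach than the one below it. As printed, the second VGPR alternative sets a ceiling on the fall in serum M-protein where a floor is expected. It therefore admits patients who have not responded and excludes the deepest falls. Nothing elsewhere in the protocol corrects it.

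The other two points concern rules that a programmer would have to resolve alone. The marrow limits for CR and for relapse from CR share the value 5%. ORR names two of the four response categories in Appendix I.

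At stake are two of the three formally compared secondary endpoints and duration of response. MRD testing, which Section 4.1 ties to reaching CR, depends on the marrow limit. The trial is open-label, so unclear rules also invite different calls at different sites.

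**Working it through.** The documents give no figure that depends on these rules, so there is none to reproduce. The check is to apply the rules literally.

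**1. VGPR serum limb.** Take a patient with secretory disease, urine M-protein 50 mg/24 h, a visible electrophoresis band, and the other PR conditions met. Classify by the fall in serum M-protein, with the sign as printed and with the sign reversed.

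| Fall in serum M-protein | As printed (≤90%) | With ≥90% |
|---|---|---|
| 0%, 10%, 30%, 49% | VGPR | SD |
| 50%, 75%, 89% | VGPR | PR |
| 90% | VGPR | VGPR |
| 91%, 95%, 99% | PR | VGPR |

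Only exactly 90% gives the same answer under both signs. As printed, no such patient can be SD. The Plateau entry in the same table treats a decrease below 50% as no significant change, so the table disagrees with itself. With ≥90% the categories run in order: below 50% SD, 50% to below 90% PR, 90% and above VGPR.

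**2. Marrow limits.** CR requires a value of at most 5; relapse from CR requires at least 5.

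- 4.9%: meets the CR limit only.
- 5.0%: meets both.
- 5.1%: meets relapse only.

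The conflict exists at one value. How often it arises depends on whether marrow counts are reported as whole numbers, which the documents do not say. The marrow item for relapse carries no confirmation step, unlike the paraprotein item. PD is listed only for patients not in CR, so relapse from CR is the only listed rule for worsening in a CR patient.

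**3. ORR as CR+PR.** An sCR patient meets CR by definition. A patient with a fall of at least 90% and urine below 100 mg also meets the PR serum limit (at least 50%) and urine limit (below 200 mg). Read as nested criteria, CR+PR therefore means PR or better, which is how Section 3.8 reports response. Read as mutually exclusive best-response labels, it loses VGPR.

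Section 3.8 gives PR or better as 90.3% (BiRd) and 79.1% (Rd), and CR as 45.8% and 13.9%. It gives no VGPR share. The exclusive reading could then give anything from 45.8% to 90.3% for BiRd and from 13.9% to 79.1% for Rd.

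**4. Illustration if VGPR as printed is counted in ORR.** Let f be the share of patients below PR who have urine M-protein under 100 mg/24 h. This is an assumption, taken as equal in both arms. Then ORR = p + f(1 − p), and the difference between arms is (1 − f) × 11.2 points.

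Power uses n = 153 per arm (Section 14.2) and two-sided alpha 0.05/3 (z = 2.394), with a pooled variance under the null. For f = 0:

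- SE under the null = √(2 × 0.847 × 0.153 / 153) = 0.0412
- SE under the alternative = √((0.903 × 0.097 + 0.791 × 0.209) / 153) = 0.0407
- Power = Φ((0.112 − 2.394 × 0.0412) / 0.0407) = 63%

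| f | BiRd | Rd | Difference | Power |
|---|---|---|---|---|
| 0 | 90.3% | 79.1% | 11.2 points | 63% |
| 0.25 | 92.7% | 84.3% | 8.4 points | 46% |
| 0.50 | 95.2% | 89.6% | 5.6 points | 29% |
| 0.75 | 97.6% | 94.8% | 2.8 points | 13% |

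**The case against.** The best defence is that few assessors would call a flat M-protein a very good partial response. Section 2.2 names the IMWG criteria, and the sign looks like a slip. VGPR is not itself an endpoint, and a 95% fall with a visible band still lands in PR, so that patient remains a responder. All of this is fair, and it limits the damage. It does not make the printed rule usable. A fault in converting the PDF to text cannot be wholly excluded either, although ≥ appears correctly in the PR and relapse entries of the same table.

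A reader might infer four stronger things that the documents do not support.

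- **That CR+PR drops the better responders.** This holds only if the labels are exclusive, which Section 14.4 does not say. It is an ambiguity.
- **That the trial loses power for ORR.** The figures mix two readings: VGPR exactly as printed, but ORR widened beyond CR+PR to include it. Under literal CR+PR, a patient with a 10% fall is neither CR nor PR and does not inflate ORR. The fractions have no source in the protocol, the base rates come from a retrospective case-matched comparison, and the trial was not sized for ORR.
- **That primary PFS is affected.** The VGPR and ORR points cannot affect it. For the marrow overlap it is not shown. Table A in Section 14.3 dates progression by hematological, radiological or urine assessments, and the text beneath it refers only to radiological assessments verified by an IRC. Neither says that a marrow value alone makes a PFS event. Follow-up marrow is also taken only to confirm remission or progression, or when clinically indicated.
- **That the CR marrow limit is the one that is wrong.** The documents show an overlap, but not which limit should move. Appendix I cites reference 35, and the reference list ends at 33.

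**Conclusion.** The VGPR serum limb is wrong as written, and Appendix I alone is enough to show it. For patients with urine M-protein below 100 mg/24 h and a visible band, it misplaces every serum fall except exactly 90%. The marrow overlap is real but confined to exactly 5%. The ORR wording is unclear rather than wrong.

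The consequences stay within secondary, exploratory response endpoints. The primary log-rank comparison, the 133 events and the 306 patients do not depend on the VGPR or ORR wording. A fall in the ORR difference from 11.2 to 8.4, 5.6 or 2.8 points shows what could happen at f = 0.25, 0.50 or 0.75 if VGPR as printed were counted as response. It is not an estimate of what will happen. The correction is worth making because the rules feed formal comparisons and cost little to repair.

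**What to change.** 1. **Appendix I, VGPR:** confirm the sign against the source document and print a reduction of at least 90% (≥90%) in serum M-protein, keeping the urine condition.
2. **Appendix I, CR and relapse from CR:** reconcile the two 5% marrow limits against the source so that no value meets both. State whether relapse from CR counts as progression for PFS.
3. **Section 14.4:** state that ORR is PR or better (sCR+CR+VGPR+PR) and that the CR rate is sCR+CR. With item 1 in place, this prevents VGPR patients from being dropped, or non-responders from being added, when best response is coded in exclusive categories.

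The cost is a few words in one appendix table, one sentence in Section 14.4 and a line on relapse from CR. No new data, visits or patients are needed. Any responses already coded from the printed rule would need to be re-derived from the same laboratory values.
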